## **Data and follow-up**

Data will remain confidential. Any protected health information (including email addresses) will be stored in an encrypted password-protected database with access granted only to IRB approved study investigators and coordinators. Surveys will be completed using Qualtrics, a password protected internet-based survey tool. We will use a portable tablet such as an iPad to allow the patient to complete the questionnaire in privacy in the ED using the Mercury secure network. This tablet will also be password protected. Texting services will be provided by a HIPAA compliant provider of text message services, RipRoad. All email will be sent from the CUMC Microsoft Outlook server from a CUMC email address (e.g. [[contact]](mailto:[contact]); the PI of this study).

The risk to loss of privacy is low. Qualitative studies suggest that adolescents do not perceive parents reading their texts as threat. Adolescents describe that their phones are usually password protected and parents do not read their texts. Additionally, in our prior studies, we demonstrated that no participant felt unsafe from receiving the text messages.

## **Potential benefits to subjects and others**

This study presents few potential risks to its participants. Instead, it presents several potential direct benefits to subjects. The patient may benefit from participation by gaining knowledge about her reproductive health. From previous studies, we know that adolescent females in our ED report not wanting to become pregnant and are interested in starting contraception. Our study connects them to reproductive services, builds self-efficacy, provides reliable factual sexual health information, supports healthy relationships, provides information on how to talk to trusted adults about sex, dispels contraceptive myths, and provides information on where to obtain birth control locally. The intervention also utilizes the psychology of motivational interviewing, which emphasizes the importance of adolescent involvement in their decision making, and incorporates sexual education from evidence-based curriculums.

## **Importance of knowledge to be gained**

The potential risks to subjects are reasonable in relation to the knowledge that will result from the study. We will learn if a user-informed, theory-based texting intervention is feasible, acceptable and potentially efficacious. Data from this study will allow us to decide if we should proceed with the conduct of a larger, multi-center RCT. We will also learn if texting is a useful way to provide adolescent ED patients with information, based on the feedback we receive. This will inform national models for health promotion both inside and outside the ED setting.

This texting intervention is automated, reproducible and scalable. As such, it could be an important vehicle to disseminate reliable sexual health information to adolescents who have unmet health needs and may not have other sources of medical care.

## **Alternatives**

Subjects do not have to participate and their clinical care will not be affected in any way.

## **Data and Safety Monitoring (as written in our K23 application)**

We will create an independent data safety and monitoring board (DSMB) consisting of 4 members not associated with the trial who have expertise in the study content area or the conduct of clinical trials. All members will be from the schools of Columbia University but will not be associated with the trial. We will monitor for any conflicts of interest.

The DSMB will primarily monitor participant safety and the scientific conduct of the trial. No interim analyses for efficacy will be undertaken. We will create a data and safety monitoring plan prior to study initiation.

The DSMB will be responsible for the following:

- Reviewing the research protocol and plans for data and safety monitoring
- Ensuring that the monitoring is timely (at least twice a year) and that those responsible for the monitoring have appropriate expertise to accomplish its mission
- Evaluating the progress of the interventional trial, including periodic assessments of data quality and timeliness, participant recruitment, accrual and retention, participant risk versus benefit, performance of the trial site, and other factors that can affect study outcome
- Conducting ongoing monitoring of the trial, with review of the protocol prior to study initiation and reviews when half of the participants are accrued and at study completion
- Ensuring that the study investigators respond to recommendations emanating from the monitoring activities
- Protecting the confidentiality of the data and the results of monitoring

Meetings will be closed and written summary reports will identify topics discussed by the DSMB and describe their individual findings, overall safety assessment and recommendations. The rationale for recommendations will be included when appropriate. This report will generally not include confidential information. The final summary report will be forwarded to NIH program officer and Principal Investigator.

We consider an Adverse Event to be any loss to confidentiality of patient data. If that occurs, the DSMB will be notified within 24 hours and a DSMB review will ensue. We also define an Adverse Event as an event where a participant feels threatened or is hurt due to the text messages we send her. This is a question we ask on our follow up phone survey. If this occurs, we will contact our DSMB. Changes will be made to the intervention or protocol accordingly.

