#### Waiver of assent with a substitute of an information sheet

Our study requests a waiver of assent with a substitute of an information sheet (**as suggested by the IRB**) to be provided to enrolled minors. The IRB may waive the requirement for the investigator to obtain a signed consent form for some or all subjects if it finds (based on 45 CFR 46.117(c)(1)):

- Principal risks are those associated with a breach of confidentiality concerning the subject's participation in the research
  - *This study collects behavioral information about the participant, such as sexual behaviors. This is sensitive information. The principal risk to the participant is confidentiality.*
- Consent document is the only record linking the subject with the research.
  - *This study does NOT collect dates of birth or HIV status. This study does collect medical record numbers and phone numbers. The only record linking the subject's name with the research would be her consent form. (We have omitted the release of medical information form to comply with this term). All patients will receive a unique identifier. Only at the time of follow-up will her name as read from the medical record; however, researchers will be blinded to any behavioral information already provided in the study by that participant.*

In addition, we believe that our study presents **MINIMAL risk**. Participants will not be exposed to the possibility of harm -- physical, psychological, social, legal, or other -- as a consequence of participation as a human subject in this research activity. This study should not increase the probability or magnitude of risks ordinarily encountered in daily life. We believe this to be true for the following reasons:

- The sexual health information we will send via mobile phone is similar to the sexual health education received in schools, which is approved by state and federal initiatives.
- The principal threats to adolescent health and well-being are social and behavioral: personal behavior and the behavior of peers. Behavioral research includes intervention programs to reduce harmful behaviors and increase protective behaviors as well as projects designed to improve understanding of the factors influencing adolescent behavior. Behavioral research generally presents little risk to the individual adolescent. Research on the prevention of HIV and teen pregnancy has resulted in more effective prevention programs to reduce sexual risk behavior.

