### **Sources of material** (same as Part 1 except for when mentioned as unique to Part 2)

Similar to our prior texting trial (**IRB #AAAM3457**), we will collect data from the EMR, a baseline survey, telephone follow-up, and mobile platform provider.

- The EMR tracking board in the ED will be used by research coordinators and investigators to identify potentially eligible patients. The EMR will also be used to collect follow-up information. (See Documents)
- A baseline survey will collect information regarding
  - Demographics (such as age and grade in school),
  - Reproductive and sexual history (such as prior use of birth control methods, age at first intercourse, and number of sexual partners),
  - Prior medical care (such as last time to a primary care provider and history of contraceptive counseling by a provider),
  - Contraceptive knowledge,
  - Decisional conflict with choosing a contraceptive method,
  - Psychosocial mediators of behavior change (self-efficacy, self-esteem, social support)
  - and pregnancy intentions (such as wanting and timing of future pregnancies).

Questions for the survey were adapted from the Youth Risk Behavioral Survey, National Survey of Family Growth, The Fog Zone (Guttmacher validated survey set) and others written *de novo* based on investigator expertise. (See Documents)

- Telephone follow-up phone calls will be completed to determine outcomes, including contraceptive initiation. (See Documents)
- Two-way text messages will be delivered and received by RipRoad, a HIPAA-compliant mobile provider. This company has been used by Columbia University researchers in the past (see studies by [name]) and has a Business Agreement with Columbia.
- Upon enrollment into the study, participants will watch two short videos and receive a link to the website, [www.dr-erica.com](http://www.dr-erica.com).
  - The first video is a short explanation of our program which can be viewed at [www.dr-erica.com/introductory.video](http://www.dr-erica.com/introductory.video).
  - The second video a video about birth control options which can be viewed at <https://vimeo.com/271757026>.

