  - In our prior qualitative interviews, we learned that adolescents receive their health information from unreliable sources, especially on the Internet. We created [www.dr-erica.com](http://www.dr-erica.com) as a one-stop website that contains reliable, medically accurate links to websites such as StayTeen.org and Bedsider.org. Topics include birth control options, local clinics, testimonials, and an introduction to who Dr.Erica is. Many of the links we sent to teens in our texts are on this site. This site contains NO Columbia identifiers, collects NO patient identifiers, and is approved by Columbia University Information Technology.

- (NEW TO THIS MODIFICATION): We will be asking for email addresses for the following two reasons:
  - Disconnected phone numbers: Adolescents often change phone numbers. If RipRoad reports that a phone number has “undelivered” texts, that is usually due to a disconnected phone number. We will email that participant (using the email template attached in Documents) to ask for an updated phone number.
  - Follow up: If a participant does not complete the follow up survey (sent via text as a link), she will be sent an email with the follow-up survey link (using the email template attached in Documents).
- All text messages are attached under Documents.
- Based on preliminary feedback from Study Part 1, we found that many adolescent text questions into the program such as “Where can I get birth control pills?”. Because this program is automated, when questions are received, we send an error message that reads, “Sorry, we do not understand that. If you are answering a question, please reread & try again. If you have general questions, check out [www.dr-erica.com](http://www.dr-erica.com).” Therefore, these questions are never answered by the program. As a solution to this, we have built in “[name] Hours.” This will work in the following manner:
  - Any incoming response (text into the program by a participant) that is 4 or more words will trigger two events:
    - A response text to the participant which reads as follows: “Sorry, I don’t understand your text. But we can answer your questions LIVE during our [name] Hours. You can text privately with a confidential health educator who can answer all your questions! [name] Hours are from 7-8pm. I’ll have her text you this week and let you both connect. In the meanwhile, check out dr-erica.com.”

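### The plan describes no way of finding its first-listed adverse event, loss of confidentiality, so a zero count could not by itself be read as evidence that no privacy was lost

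*Combined protocol and SAP*

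**What the plan says.** In the Part 2 section *Waiver of assent with a substitute of an information sheet*, the plan states: "The principal risk to the participant is confidentiality". The same section goes on to describe the main risks of such research as embarrassment and sensitive information reaching other people.

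*Data and Safety Monitoring* defines two adverse events.

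- **First event:** "We consider an Adverse Event to be any loss to confidentiality of patient data". The stated action is: "If that occurs, the DSMB will be notified within 24 hours and a DSMB review will ensue". No question, log, audit or vendor report is named that would show that it had occurred.
- **Second event:** "an event where a participant feels threatened or is hurt due to the text messages we send her". The means of finding it follows at once: "This is a question we ask on our follow up phone survey". In context, that sentence belongs to the second event.

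*Sources of material* (Part 2) gives the purpose of the calls: "Telephone follow-up phone calls will be completed to determine outcomes, including contraceptive initiation". That section and *Outcomes and Data Sources* show that follow-up also runs through a web survey, linked by text and then by e-mail for those who do not complete it.

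*Data and follow-up* asserts: "The risk to loss of privacy is low". Its support is that adolescents report parents do not look at their texts, and that nobody in the group's earlier studies felt unsafe.

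**The concern.** In a texting trial about contraception, an obvious way to lose confidentiality is for a parent or partner to read the phone. The sponsor's own privacy argument treats parents reading texts as the matter at issue. Silent reading leaves no trace in the study's systems, so it will usually be learned of only if the participant says so. The question the plan describes does not ask about it. A finding that nobody felt unsafe has the same limit, because it measures a reaction and not whether someone else saw the messages.

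Two features of Part 2 add to the importance of asking. The program is two-way, so a participant's own replies may sit on her phone, and live text hours and e-mail contact have been added. The control arm is not free of exposure either, since it receives a welcome text.

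At stake is what the monitoring board and later readers can conclude. The board looks at safety at least twice a year, at half accrual and at completion, and the trial is meant to inform a larger multi-center study. A line reporting no confidentiality events would look reassuring without having measured the most likely kind of disclosure.

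**Working it through.** **Is there a stated means of detection?** Setting the provisions side by side:

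| Event | Definition given | Action given | Means of finding it |
|---|---|---|---|
| Loss of confidentiality | Yes, but not whether a text read on the phone counts | Board notice within 24 hours, then review | None described |
| Threatened or hurt by texts | Yes | Board contacted | Question on the phone survey |

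A participant whose texts were read without threat or hurt falls in the first row if third-party viewing counts, and the question in the second row does not reach her.

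**Number of answers.** The plan gives no figure on privacy. The sample-size paragraph gives 250 enrolled and 20% loss. With 1:1 allocation (an assumption, because no ratio is stated), 125 × 0.8 = 100 per arm. This agrees with the plan's own power statement for 34% versus 17%:

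- null standard error √(2 × 0.255 × 0.745 / 100) = 0.0616
- alternative standard error √((0.17 × 0.83 + 0.34 × 0.66) / 100) = 0.0605
- power Φ((0.17 − 1.96 × 0.0616) / 0.0605) = 79.2%, against the stated 80%

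**If the question is asked and fully answered.** The chance of at least one report among 100 at a true rate *r* is 1 − (1 − *r*)^100. The rates are assumptions, since the documents give none.

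- *r* = 2%: 2 expected, 86.7% chance of at least one
- *r* = 5%: 5 expected, 99.4%
- *r* = 10%: 10 expected, above 99.9%

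The upper exact two-sided 95% limit for 0/100 is 1 − 0.025^(1/100) = 3.6%. With all 125 answering it would be 2.9%.

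**If only a share *s* of events comes to light.** The chance of recording none among 100 is (1 − *r* × *s*)^100:

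| *s* | *r* = 2% | *r* = 5% | *r* = 10% |
|---|---|---|---|
| 1 | 13.3% | 0.6% | <0.01% |
| 0.5 | 36.6% | 8.0% | 0.6% |
| 0.25 | 60.6% | 28.4% | 8.0% |
| 0.1 | 81.9% | 60.6% | 36.6% |
| 0 | 100% | 100% | 100% |

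The upper limit after a zero count becomes 3.62% / *s*: 7.2% at *s* = 0.5, 14.5% at 0.25 and 36.2% at 0.1, with no limit at *s* = 0. The plan gives no basis for choosing *s*, so a zero count cannot be converted into a statement about the true rate.

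**The case against.** The strongest reply is that the safety section speaks of patient data, and *Data and follow-up* describes that data: a database, a survey tool, a tablet, a texting vendor and institutional e-mail. On that reading, staff or the vendor detect breaches and the phone question covers harm from texts. This is coherent, and the plan does not rule it out. But the waiver section describes the risk as disclosure to others, and the privacy argument turns on parents reading texts, so the scope of the definition is left open.

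Four stronger readings are tempting, and the documents do not support them.

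- **That participants are asked about nothing except threat or hurt.** The follow-up instruments are attachments outside the text, and a separate monitoring plan is promised. Either may already ask about disclosure.
- **That a zero count would be an artefact.** Staff could find breaches of study data. Month-3 follow-up has open-ended questions in which a participant might volunteer an event. Incoming texts are recorded, so a third party who replied could be noticed.
- **That texts to a reassigned number go undetected.** The plan acknowledges that "Adolescents often change phone numbers" and has a procedure, prompted by undelivered texts, for requesting the new number by e-mail. How the vendor reports a text to a reassigned number is not stated.
- **That the trial fails to support its own privacy claim.** The low-risk statement is a prospective justification. Privacy is neither an endpoint nor a stated criterion for proceeding.

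It is also fair that a month-3 question comes after the 10-week program. It can count disclosures, but not prevent them.

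**Conclusion.** The point holds as a gap in safety ascertainment. The plan names its principal risk, makes it the first adverse event, and describes no way of finding it. Unless the attachments or the monitoring plan supply one, a zero count could not be taken as evidence of no privacy loss. The primary outcome and its analysis are unaffected.

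The size depends on the unknown share of events found. At an assumed 5% true rate among 100 participants, the chance of recording none is 0.6% with full ascertainment and 60.6% if one event in ten is found. If the question is asked, 0/100 would limit the rate to 3.6%, assuming 1:1 allocation, 20% loss and full reporting. That limit covers only disclosures the participant knows about. It says nothing about reading by a new holder of an old number, which she generally cannot know.

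**What to change.** 1. In *Data and Safety Monitoring*, state whether unwanted viewing of study texts or e-mails by a third party counts as loss of confidentiality.
2. Add one yes/no item to the month-3 follow-up, in both arms and in every mode (phone, text link, e-mail link): *Did anyone see or read a study text or e-mail that you did not want them to see?*
3. Report the number answering yes over the number asked, by arm, with an exact 95% interval, to the board and in the results.

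If an attached instrument or the monitoring plan already asks this, it is enough to cite it in the safety section and confirm that it covers both arms and all modes.

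The cost is one survey question and one line in the safety table. The downside is that some minor disclosures will be reported as adverse events and, if counted under the first definition, will trigger the existing board notice.

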## Study Procedures

Eligible enrolled patients will either text message in the ED will confirm intervention receipt (manual enrollment) or will text RipRoad for enrollment (technological enrollment). This will ensure texting capabilities.

10 participants will receive the 2 month intervention as a beta test. They will receive weekly follow-up calls to qualitatively assess real-life occurrences, such as current sexual activity, change in pregnancy intentions, and perspectives of the messages. Questions will include, “*What about the program is least or most engaging?*” and “*How have your contraceptive choices change because of the texts?*”.

Other probes may include questions about message frequency and time of day. Texts will then be refined and finalized. 40 participants will receive the complete intervention to assess feasibility and acceptability, and potential effectiveness. These participants will not be assessed weekly but rather 3 months after enrollment (week 12).

We expect that approximately 10 of the 50 participants will have technological issues with their phones such as phone disconnections. That is why we have a target accrual of 50 but an actual accrual of 40.

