## Part 2: The pilot randomized control trial

Strategy: We will conduct a pilot RCT of 250 adolescent females at high risk of unintended pregnancy to receive either the 10-week texting program, [name], or standard discharge instructions. *We hypothesize that the texting program will be feasible, acceptable, and increase contraceptive initiation rates (our primary outcome).*

Setting: We will recruit patients from the pediatric ED at New York-Presbyterian Children's Hospital, which cares for over 50,000 patients per year. Patients are predominantly Hispanic, insured, and of low socioeconomic status.

Subjects: The eligibility criteria is the same as Study Part #1. Inclusion: (1) age 14-19 years and (2) sexually active with males in the past 3 months. Exclusion: (1) currently using any "effective" form of contraception (as defined by the World Health Organization and includes the Shot, intrauterine device, ring, implantable device, Patch, birth control pills, or sterilization), (2) do not own a mobile phone with texting, (3) are pregnant, (4) are too ill for participation per the attending physician, (5) are cognitively impaired, (6) do not live locally within the 5 boroughs, Westchester, Rockland, Nassau or Suffolk counties, (7) do not speak English or (8) want to "become pregnant in the next year."

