### Outcomes and Data Sources:

Feasibility will be operationalized as the following dependent variables: (a) rate of refusal to participate (*expected <20%*), (b) opt outs (texted to stop receiving messages; *expected <5%*), (c) loss to follow up (*expected <20%*), (d) technological failures (frequency and proportion of text message “bounce backs”; *expected <20%*), (e) response to texting interactivity, as an indicator of engagement (*expected >80%*), and (f) time to reply to texting interactivity (*expected <15 sec*). Data for these outcomes will come directly from our mobile platform provider.

Acceptability will be based on participant feedback. We expect that participants will “*like*” messages (*>4* on a Likert scale) and find the intervention “*relatable*,” “*helpful*,” and “*engaging*,” when asked open-ended questions about the intervention. These outcomes will be determined during month 3, 2 weeks after the 10-week intervention, via phone follow up and web-based survey sent via text message link.

Efficacy The primary outcome is effective contraception initiation, defined as (1) patient self-reports initiation at phone follow up or via text or (2) there is electronic medical review (EMR) documentation of initiation. If there is a discrepancy between self-report and EMR documentation (e.g. received prescription but never started pills), we will prioritize self-report. We define “*contraception not initiated*” if noted by self-report to not have initiated or if lost to follow up and no evidence of initiation in EMR.

Similar to our cohort study, our second primary outcome is decisional conflict. This measures a participant’s level of commitment to choosing a birth control method and has been used in other contraceptive studies and is a validated scale. We are using the low literacy version to meet the needs of our adolescent population.

We will also conduct exploratory analyses to identify characteristics of participants who appear more likely to opt out of the study (allowing us to develop further retention strategies). Finally, we will examine texting response rates over time and how this relates to contraception initiation.

Secondary outcomes include follow-up to reproductive care clinics, pregnancy rates, an increase in condom use, talking to an adult about birth control, and psychosocial mediators of behavior change.

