Data for secondary outcomes will also be collected via phone follow up and EMR review during month 3 and interactive text messaging at weeks 3 and 6. A baseline survey will collect information regarding demographics, reproductive and sexual history, prior medical care, and pregnancy intentions. Questions were adapted from the Youth Risk Behavioral Survey, National Survey of Family Growth, and written *de novo*.

Analysis: We will analyze both an intention-to-treat (ITT) population and per-protocol population. The ITT population will include all enrolled and randomized patients. The per-protocol population will only include participants who completed follow-up and, for those in the intervention group, excludes those who received none of the text messages. Acceptability and Feasibility: We will summarize outcomes related to feasibility and acceptability using standard descriptive statistics and conduct exploratory bivariable analyses to identify characteristics of participants who appear more likely to opt out of the study (in order to develop further retention strategies). Potential efficacy: We will calculate the absolute risk difference (ARD) between groups with exact test-based 95% confidence intervals. For the ITT analysis, the outcome for those lost to follow-up will be imputed conservatively as *contraception not initiated*. We will use the chi-square test to determine the potential effect of the intervention on contraception initiation. We will conduct exploratory multivariable logistic regression analyses to test if age group (older (18-19 years) versus younger (17 and younger)), ethnicity, race, prior family planning clinic visits, having a primary care provider, prior pregnancy, and prior use of contraceptives, potentially confound or modify the effect of texting on contraception initiation. We will also examine texting response rates over time and how this relates to contraception initiation. We will also measure changes in contraception knowledge and decisional conflict based on proportions.

Sample size: Using prior ED studies, we expect to enroll approximately 250 patients over 2 years. Accounting for a 20% lost to follow up rate, this would enable us to detect a 17% absolute increase in contraception initiation

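### The only question about text-related harm that Part 2 describes comes at month 3, two weeks after the programme ends, so it cannot identify a participant while she is still receiving texts

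*Combined protocol and SAP*

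**What the plan says.** The Data and Safety Monitoring section has two kinds of adverse event. One is a loss of confidentiality, which must reach the DSMB within 24 hours. The other concerns the texts themselves: "We also define an Adverse Event as an event where a participant feels threatened or is hurt due to the text messages we send her". For the second kind, the section gives one means of finding out, "This is a question we ask on our follow up phone survey", and one action, "If this occurs, we will contact our DSMB", with no time limit. It adds that the intervention or protocol will then be changed as needed.

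Participants are randomised "to receive either the 10-week texting program" or standard discharge instructions. Outcomes and Data Sources (Part 2) dates the follow-up when it describes acceptability: "These outcomes will be determined during month 3, 2 weeks after the 10-week intervention, via phone follow up and web-based survey". Part 1's Study Procedures puts the corresponding assessment at "3 months after enrollment (week 12".

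Contacts during the programme are already planned. Secondary outcomes are collected by "phone follow up and EMR review during month 3 and interactive text messaging at weeks 3 and 6". Nothing about harm is assigned to weeks 3 and 6. Opt-outs (expected below 5%) and loss to follow-up (expected below 20%) are listed separately as feasibility outcomes. The sample-size paragraph allows for 20% loss.

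**The concern.** An adverse event caused by messages can recur with every message, so the useful time to learn of it is while messages are still being sent. These participants are aged 14 to 19, parental consent is to be waived, and the plan names confidentiality as the principal risk. If the texts cause trouble for a participant in week 1, the described question reaches her only when no programme is left to change for her.

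Two things are at stake. The first is the chance to respond to an affected participant during her own exposure. The second is what the trial can say about safety at the end: a result of no reported harm would rest only on those reached at month 3.

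**Working it through.** **Inputs.** Programme length is 10 weeks (Part 2, opening paragraph). Follow-up is in month 3, two weeks after the programme (Outcomes and Data Sources), and week 12 is stated for Part 1. Interactive texts are planned at weeks 3 and 6. Enrolment is about 250 with 20% loss (Sample size). There are two block-randomised arms; the ratio is not stated, so 1:1 is assumed.

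**The plan's own interval.** Week 12 − week 10 = 2 weeks, as stated.

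**Wait from harm to question.** For harm in week w, the wait is 12 − w:
- week 1: 12 − 1 = 11 weeks
- week 3: 12 − 3 = 9 weeks
- week 6: 12 − 6 = 6 weeks
- week 10: 12 − 10 = 2 weeks

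**Programme left when the question is asked:**
- week 3: 10 − 3 = 7 of 10 weeks (70%)
- week 6: 10 − 6 = 4 of 10 weeks (40%)
- month 3: 0 of 10 weeks

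**Participants not asked.** The TM arm has 250 / 2 = 125. At 20% loss, 125 × 0.20 = 25 are not asked and 100 are. The earlier pilot reports 88% follow-up; at 12% loss the figures would be 125 × 0.12 = 15 and 110. Both cases treat everyone followed up as having been asked. The item is described for the phone survey, so the number not asked could be larger if some participants answer only through the web link.

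**What zero reports would mean.** The one-sided 95% upper bound for 0 of n is 1 − 0.05^(1/n). For n = 100 this is 1 − 0.05^(1/100) = 3.0%; for n = 110 it is 1 − 0.05^(1/110) = 2.7%. Either bound applies to those who answered and says nothing about those who did not.

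**The case against.** The strongest reply is that harm need not wait for month 3. The Part 2 Sources of material section says that incoming texts produce an immediate email to the principal investigator and that longer ones lead to live contact. A participant can also end her own exposure by texting to stop. Both points stand. A reader might infer that no harm can surface before month 3, and the documents do not support that. What they do support is narrower: these routes are set up for answering questions and for counting feasibility, and neither is described as a way of recording adverse events.

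The reply also has force on action. Enrolment runs over two years and the DSMB monitors at least twice a year, so a month-3 report can still lead to changes that protect later participants. It comes too late only for the person reporting. Nor is the delay uniformly about three months; it is 2 to 11 weeks, depending on when the harm occurs.

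On opt-outs, a reader might infer that the plan uses them only for retention, or that those who opt out are lost. Neither is right. Opt-out is a feasibility outcome, the DSMB reviews retention, and someone who opts out can still be called at month 3. Comparing opt-outs between arms would say little, because the standard-referral arm gets only a welcome text. That those who leave are the most affected is plausible, but the documents do not show it.

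The survey, the text scripts and the separate monitoring plan are not part of the text reviewed, so an earlier harm item cannot be excluded. None is described, and the safety section names only the phone survey. The investigators also argue minimal risk and report that nobody in their prior studies felt unsafe because of the texts. That bears on how often harm is likely to occur, not on when it would be found; the earlier pilot trial used one-way messages, whereas this programme is interactive.

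**Conclusion.** The point holds for Part 2, limited to solicited harm. The one described question identifies no participant during her exposure, comes 2 to 11 weeks after the harm, and misses about 25 of 125 TM participants at the planned 20% loss (15 at the pilot's 12%). These counts assume 1:1 allocation. The timing assumes that month 3 means about week 12 and that no harm item sits in the unseen scripts.

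It does not follow that a week-3 question would give the DSMB a much larger safety sample at its half-accrual review. Texts sent cannot be compared with answers received: the earlier pilot delivered 1172 of 1654 texts (70.9%), and not every delivered text is answered. The gain is in timing. The primary analysis is unaffected, and the change is worth making because it is small and concerns an adverse event that the plan itself defines.

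**What to change.** - For the TM arm, add one neutrally worded check to the interactive texts already planned at weeks 3 and 6, and keep the month-3 question.
- In Data and Safety Monitoring, state a DSMB reporting time for text-related harm. The 24 hours already used for a confidentiality loss is one example, counted from when the study team identifies the report.
- Include TM-arm opt-out counts in the DSMB safety report.
- Word any finding of no harm as applying to those who answered.
- If a harm item already exists in the week-3 or week-6 scripts, say so in the safety section.

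**Cost.** One item is added at two existing contacts, with a few lines in the safety section and the DSMB report. A texted question could be seen by someone else, so its wording must reveal nothing; a neutral item is also less specific than the month-3 question, which is a reason to keep both. Replies need someone to read them. The existing email alert can serve, but it is listed under incoming texts of four or more words although its own sentence covers all texts, so the team should confirm that short replies trigger it. Participants who opt out or are disconnected before week 3 would still be missed by the texted item.
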